4.7 Adverse Events (AEs)

Monitoring of AEs will be completed at all visits. Briefly, any untoward events reported by the subject or observed by the study staff following the first dose of study medication are to be recorded as AEs. Any untoward events that occur prior to this time are recorded in the medical history page of the eCRF. Refer to [Section 8](#) for details regarding definitions, documentation, and reports of AEs and serious adverse events (SAEs).

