8.1.3 Reporting Procedures and Requirements for Adverse Events

8.1.3.1 Study Reporting Period for Adverse Events

At every visit or contact, study staff will ask each participant how she felt since her last visit and indirectly ask if she has experienced any AEs.

The reporting period for AEs is the period immediately following the signing of the ICF through 30 days after last use of study product.

For the purposes of study analysis, if a non-serious AE has not resolved at the end of the study-reporting period it will be reported as still ongoing in the EDC system. However, the investigator must make every reasonable effort to follow the event to resolution or stabilization and report to [REDACTED].

SAEs must be followed until resolution. Resolution of an SAE is defined as the return to baseline status or stabilization of the condition with the expectation that it will remain chronic.

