8.1.4 Laboratory Test Abnormalities

If an abnormal laboratory result indicated as clinically significant by the investigator is the reason for a subject being withdrawn from the study or requires treatment for the abnormality, this abnormal result must also be reported as an AE. In addition, any laboratory test result that meets the criteria for an SAE (see [Section 8.1.1.3](#)) must also be reported as an SAE so [REDACTED] [REDACTED] can collect additional information about that abnormality, including information regarding relationship to test article or other causes, any action taken, and outcome.

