9.7.4 Serious Adverse Events (SAEs)

Subjects with SAEs will be listed by center with the following variables included: SAE description (as reported by investigator), MedDRA “included” term, MedDRA “preferred” term, MedDRA system-organ class (based on the “include” term), start and stop days relative to the date of first dose, maximum intensity, relationship to the investigational, action taken with the study product per the investigator’s judgment, and outcome.

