3.8.2 Adverse Events and Serious Adverse Events

A treatment-emergent adverse event, (TEAE) is any symptom, sign, illness, or experience that develops or worsens in severity and/or frequency after the study treatment started. A serious adverse event (SAE) is any adverse event that results in any of the following outcomes: Death; immediate threat to life; inpatient hospitalization or prolongation of an existing hospitalization; persistent or significant disability/incapacity; congenital anomaly/birth defect; other serious (medical important) AEs. All AEs will be coded with system organ class (SOC) and preferred term (PT) from the MedDRA Version 20.0. The codings will be reviewed by qualified medical personnel.

Incidence of AEs and SAEs will be summarized by SOC and PT with the number and percentage of subjects with each SOC and PT by treatment arm. The following tables will be presented for Safety population:

- AEs by SOC and PT
- AEs that led to study discontinuation or death by SOC and PT
- AEs by SOC and PT by severity
- AEs by SOC and PT by relatedness to the study treatment
- AEs in descending order of SOC frequencies (no PT displayed)
- AEs in descending order of PT frequencies (no SOC displayed)

All the above tables (except for where specified) are counting number of distinct subjects in each SOC and PT. Subjects reporting more than one AE/SAE in each PT will be counted only once to that PT, using the most severe intensity, for unique number of subjects counting. The only exception to this will be for the summary by relatedness to the study treatment, where subjects will be counted only once using the strongest relatedness to the study treatment for the purpose of counting distinct number of subjects. The same principle also will be applied to the summary at the SOC level.

An overall AE high-level summary table will also be provided for Safety populations with total number and percentage of distinct subjects (but no SOC or PT) for

- AE severity (Mild, Moderate, Severe)
- AE relatedness (Not Related, Possibly Related, Related)
- SAE
- Death, or discontinued study due to any AE

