Another high-level summary table for Safety population will present the counts of events (not distinct subjects) as the following chart. Note that each percentage, if provided, is based on the number on the one where "(100.0)" is displayed. This AE summary table, done for each treatment group and all Safety subjects, provides the cross reference between every level of relatedness and severity.

Relatedness (to the study treatment)	AE Severity			Total # (%) of Events
	Mild	Moderate	Severe	
Not Related	xx	xx	xx	xx (x.x)
Possibly Related	xx	xx	xx	xx (x.x)
Related	xx	xx	xx	xx (x.x)
Total # (%) of Events	xx	xx	xx	xx (100.0)

Two listing-style tables, one is for SAEs, and the other is for AEs that led to premature study discontinuation, will also be presented, with the details about the event onset date, resolved date, study day of onset since the study treatment (calculated as Onset Date – Randomization Date +1), severity, outcome, medical intervention needed for the AE, and relatedness to the study treatment, as well as other supportive data such as the subject's age and number of days on the study.

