14.2.2	Analysis of Study Sensitivity	miITT
14.2.3M	Summary of Bacteriological Cure and Therapeutic Cure	miITT
14.2.3P	Summary of Bacteriological Cure and Therapeutic Cure	PP
14.2.4M	Nugent's Score and Amsel's Criteria Summary by Study Visit	miITT
14.2.4P	Nugent's Score and Amsel's Criteria Summary by Study Visit	PP
14.3.0	Treatment Exposure and Compliance	Safety
14.3.1.1	Overall Number and Percentage of Subjects with Adverse Events	Safety
14.3.1.2	Overall Number of Adverse Events by Severity and Relatedness to the Study Treatment	Safety
14.3.1.3C	Summary of Adverse Events by System Organ Class in Descending Order of Frequencies	Safety
14.3.1.3P	Summary of Adverse Events by Preferred Term in Descending Order of Frequencies	Safety
14.3.1.4	Summary of Adverse Events by System Organ Class and Preferred Term	Safety
14.3.1.5C	Summary of Adverse Events by System Organ Class and by Severity	Safety
14.3.1.5	Summary of Adverse Events by System Organ Class and Preferred Term and by Severity	Safety
14.3.1.6C	Summary of Adverse Events by System Organ Class and by Relatedness to the Study Treatment	Safety

14.3.1.6	Summary of Adverse Events by System Organ Class and Preferred Term and by Relatedness to the Study Treatment	Safety
14.3.2.1	List of Serious Adverse Events	Safety
14.3.2.2	List of Adverse Events that Led to Premature Study Discontinuation	Safety
14.3.5	Local Site Reaction	Safety
14.3.6	Vital Signs and Weight	Safety
14.3.7	Physical Examination	Safety
14.3.8	Gynecological Examination	Safety

Listing Number	Listing Title	Analysis Population
16.2.1.1	Subject Information	All Screened
16.2.1.2	Inclusion / Exclusion Criteria Not Met	All Screened
16.2.1.3	Subject Disposition	ITT
16.2.1.4	Subject Study Visits	ITT
16.2.2	Protocol Deviations	ITT
16.2.3	Subjects Excluded from the Efficacy Analysis	ITT
16.2.4.1	Demographics	ITT
16.2.4.2	Medical History	ITT
16.2.4.3	Gynecological History	ITT
16.2.4.4	Pregnancy History	ITT
16.2.4.5	Prior and Concomitant Medications	ITT
16.2.4.6	Substance Use	ITT
16.2.5.1	Drug Accountability	ITT
16.2.5.2	Treatment Exposure	ITT
16.2.6.1	Study Procedures	ITT
16.2.7.1A	Adverse Events – Part A	ITT
16.2.7.1B	Adverse Events – Part B	ITT
16.2.7.2	Local Site Reaction	ITT
16.2.8.1	Nugent's Scores	ITT
16.2.8.2	Sexual Transmitted Infection Tests	ITT
16.2.9.1	Vital Signs	ITT
16.2.9.2	Physical Examination	ITT
16.2.9.3	Gynecological Examination	ITT
16.2.9.4	Pregnancy Test	ITT

16.2.9.5	Pregnancy Notification	ITT
16.2.9.6	Pregnancy Outcome	ITT

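### The SAP defines a treatment-emergent AE but applies it to no table, so pre-dose events can enter the Safety-population AE rates; two listings also count onset day from randomization instead of first dose

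*SAP*

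**What the plan says.** **SAP.** Section 3.8.2 opens with a TEAE definition: an event or "experience that develops or worsens in severity and/or frequency after the study treatment started". The term does not appear again. The incidence tables are introduced with "Incidence of AEs and SAEs will be summarized by SOC and PT with the number and percentage of subjects with each SOC and PT", and every table named there counts AEs or SAEs. The titles in SAP 5.2 do the same, for example "Summary of Adverse Events by System Organ Class and Preferred Term". No filter on onset is stated. The two listing-style tables, for SAEs and for AEs leading to discontinuation, give a "study day of onset since the study treatment (calculated as Onset Date" minus the randomization date, plus one.

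**Protocol.** Section 8.1.3.1 says "The reporting period for AEs is the period immediately following the signing of the ICF". Section 4.7 records as AEs only events after the first dose and adds: "Any untoward events that occur prior to this time are recorded in the medical history page of the eCRF". Section 8.1.4 says that a clinically significant laboratory result that leads to withdrawal or "requires treatment for the abnormality, this abnormal result must also be reported as an AE". For SAEs, 9.7.4 asks for "start and stop days relative to the date of first dose".

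**The concern.** Evaluating safety and tolerability is the only secondary objective, and Protocol 8 names AE collection and analysis as the main way to assess safety. Arm-wise AE incidence is thus the principal safety result. If the AE dataset holds events that began before any gel was used, and no table removes them, the reported rates mix baseline conditions with events on treatment.

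With about 40 sites, different sites could follow different protocol sections. A TEAE filter in the SAP would make that harmless, and it is missing. The onset-day formula raises a second problem: a column labelled as time since treatment can show a positive day for an event that came before treatment.

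**Working it through.** **Step 1. What each section does with a pre-dose event.**

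| Protocol section | Effect |
|---|---|
| 4.7 | Not an AE; goes to medical history |
| 8.1.1.1 | An AE is an adverse change after first administration |
| 8.1.3.2 | A condition present before study entry is an AE only if it worsens |
| 8.1.3.1 | AE reporting is open from consent |
| Synopsis and Table 3 | AEs are assessed at Visit 1, before the first dose at bedtime that night (3.5.2) |
| 8.1.3.3 and 8.1.3.5 | SAEs are reportable from consent even before dosing, and each needs a matching AE record |
| 8.1.4 | A treated, clinically significant laboratory result is an AE, with no limit on timing |

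**Step 2. Three cases, each in a woman who is later dosed and so belongs to the Safety population.**

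1. *Pre-dose SAE.* 8.1.3.3 and 8.1.3.5 put it in the AE data, and no SAP rule takes it out of the tables. This is the clearest route.
2. *Non-serious event between consent and first dose.* It is an AE under 8.1.3.1 and medical history under 4.7.
3. *Positive Visit 1 chlamydia or gonorrhea swab.* The sample precedes dosing and goes to a central laboratory. SAP 3.4 removes women who later prove positive from the mITT but not from the Safety population. If the result is treated, 8.1.4 makes it an AE; 8.1.3.2 says that it is not one unless the condition worsens.

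**Step 3. Size (illustration only).** The documents give no rate of pre-dose events or of positive swabs. Let *p* be the assumed share of dosed women with such an event entered as an AE, and *b* the true share with any TEAE. If the two are independent, the reported any-AE rate is b + (1 − b)p, because subjects are counted once. The arm size is 246 (Protocol 3.1), with all women taken as dosed. The values b = 10% and 20% are assumptions; 39% is the related-event share in the label summary (195/505, Protocol 3.5.3.4.1).

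| p (assumed) | Women per arm (246 × p) | b = 10% | b = 20% | b = 39% |
|---|---|---|---|---|
| 1% | 2.5 | 10.9% | 20.8% | 39.6% |
| 5% | 12.3 | 14.5% | 24.0% | 42.1% |
| 10% | 24.6 | 19.0% | 28.0% | 45.1% |

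The addition is (1 − b)p, so p itself is the upper figure. If the entire planned 12.4% mITT loss were swab positives, that would be 246 × 0.124 = 30.5 women per arm. But 12.4% is a planning assumption that also covers baseline Nugent scores below 4. It is neither an estimate of infection nor a bound on it.

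**Step 4. Onset day.** As written, day = onset − randomization + 1. Counted from first dose, day = onset − first dose + 1. The difference is first dose − randomization.

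- First dose on the randomization day: difference 0.
- First dose on Day 3, event on Day 4: 4 as written, against 4 − 3 + 1 = 2.
- First dose on Day 3, event on Day 2: 2 as written, although no treatment had been taken; from first dose it is 2 − 3 = −1.

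The two-day start limit in SAP 3.4 applies to the PP population only. The Safety population has none.

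**The case against.** The strongest reply is that the protocol already keeps most pre-dose events out. Sections 4.7 and 8.1.1.1 start AEs at first dose, and 8.1.3.2 addresses the swab example almost directly. If sites follow these, the AE tables are treatment-emergent in practice. Tabulating all AEs also matches Protocol 9.7.1, which promises summaries of every reported AE. The table shells are a separate document not available here and could carry a filter. No AE hypothesis test is planned, and investigators can mark such events as not related. The onset-day point touches two listings that also print the onset date, and the two dates coincide for women who start the same night as instructed. Protocol 9.7.4 covers SAEs only.

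Much of this stands. A reader might infer that a Visit 1 infection *will* be counted as an adverse event of the assigned gel. The documents do not support that: it happens only where 8.1.4 is applied over 4.7, 8.1.1.1 and 8.1.3.2. A reader might also infer a bias in favour of one product. Randomization makes the added events similar in expectation across arms, so that does not follow either.

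The reply does not remove the conflict with 8.1.3.1, or the requirement that a pre-dose SAE have an AE record. It does not explain why the SAP defines a TEAE that it never uses. And the onset-day formula contradicts its own label however sites read the protocol.

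**Conclusion.** The point holds in a limited form. The SAP does not restrict any AE table to TEAEs, and the protocol is inconsistent on when AEs begin, so pre-dose events can enter the Safety-population tables. A pre-dose SAE in a woman later dosed is the clearest case; a treated positive Visit 1 swab is possible but uncertain. The size cannot be derived from the documents. Under the stated assumptions the any-AE rate rises by at most the share of women affected. The consequence is inflated absolute rates and a less clean comparison, with no expected direction between arms.

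Separately, and without any assumption about site behaviour, the onset day in the SAE and discontinuation listings is wrong by the delay in first dose for every woman who started after the randomization day. For SAEs it departs from Protocol 9.7.4; for discontinuations it contradicts only the SAP's own label. Both matters should be corrected. Neither touches the equivalence or superiority conclusions.

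**What to change.** In the SAP:

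- Base all AE incidence tables on TEAEs, meaning onset or worsening after first dose. The treatment start date is already used in SAP 3.8.1.
- Add a rule for events on the first-dose day before the bedtime dose, since the date alone cannot separate them, and one for partial or missing AE onset dates. The imputation rules in SAP 3.5.6 cover medications only.
- State which date stands in for first dose in women whom SAP 3.4 keeps in the Safety population with unknown drug accountability.
- List pre-dose AEs and SAEs separately, so that all reported AEs are still presented as Protocol 9.7.1 promises.
- Compute onset day as onset date minus first-dose date plus one for onset on or after first dose, and show earlier onsets as negative days.
- State how positive Visit 1 swabs are classified, consistent with Protocol 8.1.3.2.

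Protocol 4.7, 8.1.1.1, 8.1.3.1, 8.1.3.2 and 8.1.4 should be reconciled around one stated start point. That is a protocol amendment with IRB submission by each site. The SAP rules do not depend on it and give interpretable tables either way.

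The SAP part costs some wording, a derived flag and one changed formula. Reported AE rates may be slightly lower.

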3.4 Withdrawal of Subjects

Subjects may withdraw from the study at any time or be withdrawn from the study at the discretion of the investigator should any untoward effects occur. In addition, a subject may be withdrawn by the investigator or the sponsor if she deviated from the protocol or for other safety reasons.

Subjects withdrawing from the study will not be replaced, regardless of the reason for discontinuation. All reasonable efforts should be made to contact the subject if she decides to discontinue study treatment.

The procedures noted in the Schedule of Assessments ([Table 3](#)) should be performed for the Early Termination Visit, whenever it occurs. A subject will be considered to have completed the study after completing the Test of Cure Visit (Visit 3). If a subject is discontinued at any time after entering the study, the investigator will make every effort to see the subject and complete the early discontinuation assessments as shown in Schedule of Assessments ([Table 3](#)) and [Section 5.4](#).

A termination electronic case report form (eCRF) page should be included for each subject who receives study medication, whether or not the subject completes the study. The reason for any early discontinuation should be indicated on the form. The primary reason for a subject withdrawing prematurely should be selected from the list provided in [Section 6.2](#).

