3.5.3.4 Adverse Events

3.5.3.4.1 Clinical Trials

There were no deaths or serious adverse events related to drug therapy in clinical trials involving 800 non-pregnant women who received metronidazole vaginal gel.

In a randomized, single-blind clinical trial of 505 non-pregnant women who received metronidazole vaginal gel once or twice a day, 2 patients (one from each regimen) discontinued therapy early due to drug-related adverse events. One patient discontinued drug because of moderate abdominal cramping and loose stools, while the other patient discontinued drug because of mild vaginal burning. These symptoms resolved after discontinuation of drug.

Medical events judged to be related, probably related, or possibly related to administration of metronidazole vaginal gel once or twice a day were reported for 195/505 (39%) patients. The incidence of individual adverse reactions were not significantly different between the two regimens.

Unless percentages are otherwise stipulated, the incidence of individual adverse reactions listed below was less than 1%:

- Reproductive: Vaginal discharge (12%), Symptomatic Candida cervicitis/vaginitis (10%), Vulva/vaginal irritative symptoms (9%), Pelvic discomfort (3%)
- Gastrointestinal: Gastrointestinal discomfort (7%), Nausea and/or vomiting (4%), Unusual taste (2%), Diarrhea/loose stools (1%), Decreased appetite (1%), Abdominal bloating/gas; thirsty, dry mouth
- Neurologic: Headache (5%), Dizziness (2%), Depression
- Dermatologic: Generalized itching or rash
- Other: Unspecified cramping (1%), Fatigue, Darkened urine

In previous clinical trials submitted for approved labeling of Metronidazole Vaginal Gel the following was also reported:

- Laboratory: Increased/decreased white blood cell counts (1.7%)

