6.1 Completion of the Study

Subjects who complete the 5-day treatment and all of the evaluations at the Assessment of Clinical Cure Visit (Visit 3) will be considered to have completed the study.

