8.1.3.2 Recording of Adverse Events

AEs will be reported in the EDC system using a recognized medical term or diagnosis that accurately reflects the event. Information recorded in the EDC system must be substantiated in the source documents. All AEs must be recorded in the participant's source documents and must include the following information (when applicable):

- Specific condition or event.
- Possible etiologies and whether the event meets criteria as an SAE and therefore requires immediate notification to the sponsor. (See [Section 8.1.1.3](#) for the definition of SAEs.)
- Indication of whether the condition was preexisting prior to study entry or not and if yes, whether it has worsened in severity or frequency, in which case it is reported as an AE. Conditions present prior to study entry that do not worsen in severity are not considered AEs.
- Date of occurrence.
- Date of resolution. If the event has not resolved at the end of the study-reporting period, it will be reported as still present in the EDC system.
- AEs that change in intensity are recorded at the most severe intensity level that is reported by the participant.
- Relationship to study product as evaluated by the investigator (causality assessment).
- Action taken with the study product per the investigator medical judgment (study product interrupted, discontinued or none) and outcome.
- Seriousness: An SAE, in accordance with 21 CFR 312.32 (a), means “any adverse event occurring at any dose that results in any of the following outcomes: death, a life threatening adverse drug experience, inpatient hospitalization or prolongation of existing hospitalization, a persistent or significant disability/incapacity or a congenital anomaly/birth defect. Important medical events that may not result in death, be life-threatening or require hospitalization may be considered a serious adverse drug experience when, based upon appropriate medical judgment, they may jeopardize the patient or subject and may require medical or surgical intervention to prevent one of the outcomes listed in this definition. Examples of such medical events include allergic bronchospasm requiring intensive treatment in an emergency room or at home, blood dyscrasias or convulsions that do not result in inpatient hospitalization or development of drug dependency or drug abuse.” In addition, cancer and drug overdose are included in [REDACTED] classification of an SAE.

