9.7.1 Adverse Events

Safety will be evaluated by incidence of premature discontinuations and AEs. Summaries will be provided for all AEs reported, and separately for AEs leading to study discontinuation. Serious AEs will be listed separately and described by narrative.

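### Stopping the gel because of an adverse effect is not reliably counted and is not tabulated by reason, because the AE discontinuation outputs cover only leaving the study and the completion and local-reaction rules conflict

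*SAP*

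**What the plan says.** Protocol 9.7.1 makes discontinuation one of two named safety measures: "Safety will be evaluated by incidence of premature discontinuations and AEs". The same section goes on to ask for a separate summary only of AEs that lead to leaving the study.

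The SAP follows that wording. Section 3.8.2 plans "AEs that led to study discontinuation or death by SOC and PT", a row in the overall summary for "Death, or discontinued study due to any AE", and two listing-style tables, of which "the other is for AEs that led to premature study discontinuation" (Table 14.3.2.2). SAP 3.2 takes premature discontinuation from the Disposition page of the CRF.

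The protocol gives two rules for who completed:
- Section 3.4: "A subject will be considered to have completed the study after completing the Test of Cure Visit (Visit 3".
- Section 6.1: "Subjects who complete the 5-day treatment and all of the evaluations at the Assessment of Clinical Cure Visit (Visit 3" count as completers.

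Protocol 8.1.3.2 lists, among the items to be documented for AEs when applicable, "Action taken with the study product per the investigator medical judgment (study product interrupted, discontinued or none) and outcome". Section 8.1.1.4 also puts action taken in the AE report and explains that this information serves to compare adverse reactions between the test articles.

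Protocol 4.7.1 and 8.1.1.2 and SAP 3.8.3 collect local site reactions separately from AEs. They name two triggers for recording one as an AE: it needs medical intervention, or it extends beyond the treatment area. Section 8.1.1.1 defines an AE much more broadly, as any adverse change from baseline after the first dose.

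**The concern.** Stopping study drug and leaving the study are different events, and this design separates them easily: 5 nights of dosing, then visits at 7 to 14 and 21 to 30 days after randomization. A woman who gives up the gel on night 2 has every opportunity to attend both visits.

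Safety and tolerability form the only stated secondary objective. Of the discontinuation measures, the more informative one for a 5-night vaginal gel is how many women stopped using it and why. The planned outputs answer a different question, how many left the study. Whether a woman who stopped the gel is caught even there depends on which completion rule the Disposition page follows and, for a local reaction, on which recording rule the site applies. Two sites following the protocol could count the same woman differently.

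**Working it through.** **Step 1. Do any planned outputs count stopping the drug by reason?** In SAP 3.8.2, the SOC/PT table, the overall summary row and the listing-style table all refer to the study. In SAP 5.2, Table 14.3.2.2 does the same. No table title mentions discontinuation or interruption of study drug. Two related gaps appear in the same check. The SOC/PT table promised in 3.8.2 has no entry in the 5.2 table list. The SAE listing described in 3.8.2 does not name action taken, although protocol 9.7.4 asks for it.

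**Step 2. Trace two cases through the rules.** The protocol's label summary (3.5.3.4.1) describes two women who stopped therapy: one with moderate abdominal cramping and loose stools, "while the other patient discontinued drug because of mild vaginal burning". Both resolved after stopping. Suppose each takes 2 doses in this trial and attends Visit 3.

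| Question | Cramping and loose stools | Mild vaginal burning |
|---|---|---|
| Recorded as an AE? | Yes (8.1.1.1) | Not required by 4.7.1; yes under 8.1.1.1 |
| Completed, by 3.4? | Yes | Yes |
| Completed, by 6.1? | No | No |
| In Table 14.3.2.2? | Not under 3.4; possibly under 6.1, if the CRF records it as an AE-related study discontinuation | The same, and only if the burning was recorded as an AE |
| In Table 14.3.0? | 2/5 × 100% = 40%, in the below-60% band, no reason | The same |
| In Table 14.3.5? | No | Only if rated present at Visit 2 or 3 |

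On the last row, 4.7.1 has the subject queried for presence at Visits 2 and 3. Protocol Table 1 places Visit 2 no earlier than Day 7, at least 7 − 5 = 2 days after the last planned dose, and longer for a woman who stopped early. Burning that cleared on stopping could be rated absent.

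**Step 3. How many women?** The plan states no expected figure, so the only available input is the label's 2 of 505 who stopped therapy for drug-related AEs.

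- Rate: 2/505 = 0.396%; exact 95% interval 0.05% to 1.42%.
- Per arm: 246 × 2/505 = 0.97; over the interval, 246 × 0.00048 = 0.1 to 246 × 0.01423 = 3.5.
- Two active arms: 492 × 2/505 = 1.95.
- Chance of at least one in an arm: 1 − (1 − 2/505)^246 = 0.62.

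With about one event expected per arm, a single missed case can turn a count of one into zero.

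**Step 4. Does the design change?** No. The outputs at issue are descriptive. The 603 required and 738 planned subjects rest on cure rates and mITT exclusions (protocol 9.1), which this point does not touch.

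**The case against.** Several points on the other side are sound and limit the finding.

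- A reader might infer that stopping the gel is never counted as a discontinuation. The documents do not support that. Under 6.1 she is a non-completer, and the Disposition page, whose wording is not in the documents, may capture her. Protocol 9.7.3 lists subjects discontinued due to an AE, with a narrative, and does not say whether from drug or from study.
- A reader might infer that mild burning would be no AE. Section 8.1.1.1 would make it one, and 4.7.1 says which local reactions should be documented as AEs without forbidding others. Appendix 2 tells women not to stop unless directed and to consult the study doctor for significant irritation, and the unscheduled visit in 5.5 records reactions since the last visit. The rules are in tension; the case is not certain to be lost.
- A reader might infer a bias toward no difference between arms. Nothing shows that under-recording would differ by arm, and no between-arm safety test is planned.
- Much of the signal is tabulated by arm: seven local reactions at Visits 2 and 3, doses used, days used and compliance bands. All CRF panels are also listed.
- Section 8.1.3.2 carries the qualifier that items apply when applicable, so it does not prove that the eCRF holds action taken for every AE.

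The gap that remains is the tabulated link between the reason and the stopping, together with a contradiction in the completion rules that the SAP leaves open.

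**Conclusion.** The point holds as a reporting gap in the secondary safety objective. Following the plan as written can give a wrong or inconsistent count on a safety measure that protocol 9.7.1 names, and no planned table shows why women stopped the gel.

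The size is small: about 1 woman per arm of 246, with a range of 0.1 to 3.5. This assumes that the label rate carries over. That rate comes from a single-blind trial, pools once- and twice-daily dosing whereas this trial doses once daily, and counts only drug-related events. It also assumes that women who stop the gel still attend Visit 3, for which the documents give no rate.

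The primary equivalence test, the comparisons with placebo and power are unaffected. A woman with fewer than 5 doses leaves the PP population in any case, unless she discontinued for lack of efficacy after at least 3 doses. Recording the reason for stopping reliably therefore also helps to explain who left PP.

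**What to change.** 1. In SAP 3.8.2 and 5.2, add a by-arm table and a list of AEs leading to discontinuation or interruption of study drug, taken from the action-taken field and placed beside the study-discontinuation outputs. First confirm that the eCRF captures that field for all AEs.
2. Reconcile protocol 3.4 with 6.1 so that one definition of study completion applies, say in SAP 3.2 which one the Disposition page follows, and report treatment completion separately from study completion.
3. Reconcile the local-reaction recording rule (protocol 4.7.1 and 8.1.1.2, SAP 3.8.3) with 8.1.1.1, so that a local reaction leading a woman to stop study drug is recorded the same way at every site. This concerns recording only and changes no clinical rule.

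The cost is one table, one list, short text changes and possibly one added data-capture item, since the two follow-up CRF questions in SAP 3.8.3 do not ask about stopping the gel. Reported AE and discontinuation counts may rise slightly. Sample size and primary analysis stay as they are.
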